7.2 Statistical Methods

General linear mixed models (GLMM) will be used to test the primary and secondary hypotheses in longitudinal analyses:

Primary Hypotheses

Compared to control participants, treated participants will show larger changes over time on SRS-2 total scores from Baseline to Week 12, and differences will not be maintained after treatment discontinuation at Week 12 through the end of the follow-up period at Week 16.

GLMM analyses will describe individual patterns of change over time on the SRS-2 Total score. Individual intercepts and slopes will be estimated as random-effects variables, and will be allowed to correlate. The SRS-2 scores from Baseline, Week 4, 8, 12, and 16 will be modeled as a function of treatment, time, time x treatment and will include covariates of age-stratum and the SRS-2 total score from screening. In addition to time, we will add a time-varying variable representing treatment phase (0=treatment, 1=follow-up period) and we cross this variable with treatment, time, and treatment x time. Time will be centered at Week 12. Of interest will be the main effect of treatment (i.e., treatment impact at end of active treatment), treatment x time (i.e., treatment impact on change over time during the active treatment phase), and treatment x time x treatment phase (i.e., treatment differences in change over time during follow-up period). We will use an unstructured covariance matrix. We will first test for any differences between groups across all four groups using a 4 degree of freedom linear contrast of the model parameters. If this overall test is significant at the 5% level, we will then test for differences separately at each time point. We will also report estimated mean differences along with 95% confidence intervals.

Secondary Hypotheses

Compared to control participants, treated participates will show larger changes over time on CGI Severity and RBSR scores from Baseline to Week 12 and will show reduction in those gains after discontinuation through the end of the follow-up period at Week 16.

Compared to control participants, treated participates will show larger changes over time on subscales when treatment impacts were observed on the total scores on the SRS-2, CGI Severity, and RBSR from Baseline to Week 12 and will show reduction in those gains after discontinuation through the end of the follow-up period at Week 16.

Similar GLMM analyses will be conducted to examine the longitudinal assessments of CGI Severity and RBSR and of subscales if the total scores show treatment impacts.

Exploratory Hypotheses

We hypothesize that treatment with sulforaphane will result in greater diversity of gut microbial species and a higher ratio of Bacteroidetes to Firmicutes spp. compared to placebo, and that these alterations in gut microbiota will be positively associated with behavioral improvements in the sulforaphane treatment group.

We will utilize Genotek's validated wet-lab and metagenomic data analytic pipeline for the batched sample processing and data analysis. Microbial DNA will be extracted and amplified using PCR, and 16S rRNA gene sequencing will be performed using the Illumina MiSeq platform. A curated taxonomic database will be used to assign a taxonomic classification to the sequencing reads. The mean (%) relative abundance of microbial phyla and genera will be calculated for the sulforaphane and placebo groups pre- and posttreatment. The percent change in Bacteroidetes to Firmicutes (B:F) ratio from baseline to endpoint will be compared between treatment groups using Analysis of Covariance (ANCOVA), with baseline B:F ratio included as a covariate.

Microbiota diversity and relative abundance will be assessed using conventional within sample ("alpha diversity") and between-sample ("beta diversity") metrics. Three metrics will be used to assess change in alpha diversity over time: the absolute number of operational taxonomic units (OTUs), Chao1 estimator, and Shannon index. We will use ANCOVA to test for significant differences in alpha diversity from baseline to endpoint within each treatment group. Beta diversity will be assessed with 3 metrics: Bray-Curtis dissimilarity, Weighted Unifrac distance, and Unweighted Unifrac distance. These indices will be used to determine the variance in an individual over time and the mean dissimilarity between individuals in each group. Weighted Unifrac distance distance will be used for Principal Coordinates Analysis (PCoA). We will create a PCoA plot to visually identify whether samples from each treatment group cluster together at different time points (before and after treatment). This can help determine whether any changes identified during beta diversity analysis are directed changes or random noise.

We will utilize our behavioral data collection to determine if changes in microbiota diversity and relative abundance are associated with behavioral improvement. Linear mixed models will be used to determine if microbiota composition changes over time covary with change in behavioral outcome scores.

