Statistical Methodology	General linear mixed models will be used to test the primary and secondary hypotheses; of interest will be the main effect of treatment, treatment x time, and treatment x time x treatment phase. Analyses will include data from all randomized subjects who received at least one dose of study medication and participated in at least one post-baseline efficacy assessment.		

1 Introduction

This document is a protocol for a human research study. This study is to be conducted according to US and international standards of Good Clinical Practice (FDA Title 21 part 312 and International Conference on Harmonization guidelines), applicable government regulations, and University of North Carolina research policies and procedures.

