Vital signs and reports of adverse events will be monitored at each study visit (Baseline, Week 4, Week 8, Week 12, Week 16) for tolerability and safety monitoring. A phone call with the subject's caregiver at Week 2 of the treatment phase will also be used to monitor for early adverse events. Physical exam and phlebotomy for routine laboratories (Complete Blood Count (CBC); Comprehensive Metabolic Panel (CMP); Liver Function Tests (LFTs), and Thyroid Stimulating Hormone (TSH)) will be conducted at Baseline and Week 12 for the purposes of safety monitoring. Fecal samples will be collected at home in the 48 hr prior to Baseline and Week 12 visits for microbiota analyses.

Schematic Diagram of Study Events:

¹ Behavioral outcome measures (SRS-2, ABC, CGI, RBSR)

²Adverse Events Review

³ Blood chemistries (Comprehensive Metabolic Panel, Liver Function Tests, Thyroid Stimulating Hormone)

Primary Study Endpoints

The primary study endpoint will be percent change in mean SRS-2 total scores from Baseline to Week 12, the end of the active treatment phase.

Secondary Study Endpoints

- Percent change in mean SRS-2 total scores from Week 12 (the end of the active treatment phase) to Week 16 (the end of the discontinuation phase)
- Percent change in mean SRS-2 subscale scores (Social Awareness, Social Cognition, Social Communication, Social Motivation, and Restricted Interests/ Repetitive Behaviors) from Baseline to Week 12 and from Week 12 (the end of the active treatment phase) to Week 16 (the end of the discontinuation phase)
- Change in mean CGI-Severity score from Baseline to Week 12 and from Week 12 (the end of the active treatment phase) to Week 16 (the end of the discontinuation phase)
- Proportion of participants with CGI-Improvement (CGI-I) scores of 1 (very much improved) or 2 (much improved) in each treatment arm at Weeks 12 and Week 16
- Percent change in mean RBSR total scores from Baseline to Week 12 and from Week 12 (the end of the active treatment phase) to Week 16 (the end of the discontinuation phase).
- Percent change in mean ABC subscale scores (Social Withdrawal, Hyperactivity, Inappropriate Speech, Stereotypy, and Irritability) from Baseline to Week 12 and from Week 12 (the end of the active treatment phase) to Week 16 (the end of the discontinuation phase)

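### The plan has no valid stated test for its prediction that the SRS-2 difference is lost by Week 16: the three-way term is aliased, and a non-significant Week 16 comparison cannot show loss

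*Combined protocol and SAP*

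**What the plan says.** The primary hypothesis in section 7.2 has two parts: a larger change on active treatment from Baseline to Week 12, and then "differences will not be maintained after treatment discontinuation at Week 12 through the end of the follow-up period at Week 16".

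The plan has four elements that bear on the second part.

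- **Model term.** Section 7.2 adds a "time-varying variable representing treatment phase (0=treatment, 1=follow-up period") and crosses it with treatment, time and their interaction, with time centred at Week 12. One effect of interest is "treatment x time x treatment phase (i.e., treatment differences in change over time during follow-up period"). The Study Summary repeats the list: "of interest will be the main effect of treatment, treatment x time, and treatment x time x treatment phase".
- **Testing sequence.** A 4-df overall test comes first. If it is significant at 5%, "we will then test for differences separately at each time point".
- **Estimates.** "We will also report estimated mean differences along with 95% confidence intervals".
- **Endpoint.** The secondary endpoints in section 3.1 include "Percent change in mean SRS-2 total scores from Week 12 (the end of the active treatment phase) to Week 16".

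The secondary hypotheses on CGI-Severity and RBSR are worded differently. There, treated participants "will show reduction in those gains after discontinuation".

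No section says which of these results decides whether the SRS-2 difference was maintained, and none gives a margin for it.

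**The concern.** The clause predicts that a difference disappears. A test of difference at Week 16 can reject equality, but failing to reject does not show that the arms have become alike, or that the gap has narrowed since Week 12. A claim of loss needs a comparison of the Week 12 and Week 16 differences. The term that seems meant for this is the three-way interaction, so the question is whether it can be estimated and whether it measures loss.

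At stake is the claim about what happens when treatment stops, which is the purpose of the blinded discontinuation phase. If neither route works, that claim rests on an unestimable coefficient or on the imprecision of a single visit.

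**Working it through.** **Inputs.** Section 7.1: 27 per arm; mean differences 7, 20, 18.4 and 0.4 at Weeks 4, 8, 12 and 16; SD 20; within-person correlation 0.5; at most 15% loss (27 x 0.85 = 22.95, about 23 per arm); two-sided 5%. Section 3.1: visits at Baseline and Weeks 4, 8, 12 and 16, with Week 12 ending treatment.

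**1. The plan's own figure.** For the 4-df test, the noncentrality is (n/2) d'V⁻¹d, with V compound symmetric (SD 20, correlation 0.5), and d'V⁻¹d = 1.841. At n = 27 this is 13.5 x 1.841 = 24.9. Power from the noncentral F with 52 df is 0.98; at 23 per arm (44 df) it is 0.95. The stated figure of at least 80% holds. It concerns the overall test and says nothing about loss after Week 12.

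**2. Is the three-way term estimable?** Phase is 1 only at Week 16, where centred time is 4. So phase x time = 4 x phase, and treatment x phase x time = 4 x treatment x phase. The fixed effects (intercept, treatment, time, treatment x time, phase, and phase crossed with the last three) give 8 columns of rank 6. The three-way coefficient cannot be separated from treatment x phase. Only a combination can be estimated:

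- C = β(treatment x phase) + 4 β(three-way)

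**3. Does a reduced model rescue it?** Keeping only the three-way term for the follow-up difference puts a knot at Week 12, and the coefficient becomes a change in slope. Suppose the difference grows linearly to 18.4 by Week 12 and is then fully maintained. The slope is 18.4/12 = 1.53 points per week before Week 12 and 0 after it, so the coefficient is -1.53. Equivalently, C = 18.4 - (18.4 + 4 x 1.53) = -6.1. Either way the term suggests loss when none has occurred.

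**4. What is estimable.** The change in the treatment difference from Week 12 to Week 16 is 4 β(treatment x time) + C. Adding its row to the design matrix leaves the rank at 6, so it is identified even in the model as written.

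**5. The Week 16 comparison alone** (two-sample t, unadjusted).

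- SE = 20 x √(2/27) = 5.44; half-width = 2.007 x 5.44 = 10.9 points.
- At 23 per arm: SE = 20 x √(2/23) = 5.90; half-width = 2.015 x 5.90 = 11.9 points.

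| True Week 16 difference | Non-significant, 27 per arm | Non-significant, 23 per arm |
|---|---|---|
| 9.2 (half of 18.4; assumed) | 62% | 67% |
| 13.8 (three quarters; assumed) | 30% | 37% |
| 18.4 (all) | 9% | 14% |

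**6. The direct contrast.** The SD of a within-person change is 20 x √(2(1 - 0.5)) = 20, so the SE is again 5.44 (5.90). For the planned loss of 18.4 - 0.4 = 18.0 points, power is 90% (85% at 23 per arm). At 23 per arm, varying the correlation from 0.3 to 0.7 gives 71% to 97%.

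**The case against.** The strongest reply is that the plan already looks beyond Week 16 in isolation. It names a term for change during follow-up, lists Week 12 to Week 16 change as an endpoint and promises confidence intervals. All of that is true, and it rules out two stronger readings that a reader might infer. One is that the separate Week 16 comparison is the plan's only test; the three-way term is named in both section 7.2 and the Study Summary. The other is that a non-significant Week 16 result will be taken as proof that the effect has gone; no section says so, and the planned intervals would show the imprecision. Neither reading is part of this point.

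These elements still do not supply a test. The term is aliased as specified. Coding Week 12 as follow-up would restore full rank (8 of 8), but it contradicts the definition of Week 12 as the end of active treatment, and the term would still measure a change in slope. The Week 12 to Week 16 endpoint is a percent change in means that section 7.2 does not tie to this hypothesis. The intervals have no rule attached.

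Three further replies have force.

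- **The contrast is estimable despite the aliasing.** Correct, and that is why the fix is cheap. The plan does not name it.
- **The stakes are limited.** The primary objective is superiority, and the primary endpoint stops at Week 12. This stands.
- **The percentages may be too high.** The model adjusts for screening SRS-2. If SD 20 is for raw scores and the 0.5 correlation extends to screening (both assumptions), the residual SD is 20 x √(1 - 0.25) = 17.3. The half-width is then 9.5 (10.3 at 23 per arm), and non-significance at 9.2 points falls to 52% (58%). The size shrinks; the logic does not change.

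**Conclusion.** The point holds in a limited form. The loss-of-effect clause of the primary hypothesis has no valid stated test: one named route is not estimable with a single follow-up visit, and the other cannot establish loss through non-significance. This is more than a missing detail, because following section 7.2 literally leads to one of those two routes.

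The size depends on the section 7.1 values applying at Weeks 12 and 16 and on an illustrative half-persistence of 9.2 points, which is not in the documents. On that basis the Week 16 test would miss the persisting effect in about 62% to 67% of trials unadjusted, or 52% to 58% under the adjusted assumptions above. Complete persistence would usually be detected, with 9% to 14% missed unadjusted. Week 12 efficacy inference is not affected. The change is worth making before analysis, since the direct contrast is well powered for the loss that the plan assumes.

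**What to change.** In section 7.2:

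1. Reword the second part of the primary hypothesis as: the treatment difference will decrease from Week 12 to Week 16. This matches the form of the secondary hypotheses.
2. Replace the three-way term as the test of that clause with the between-arm contrast of the Week 16 minus Week 12 change, reported with its 95% CI. Remove the redundant phase terms, or write the contrast out as the linear combination in step 4 of the working, so that the result does not depend on which column the software drops.
3. Report the Week 16 difference as an estimate with its CI, and state that it is not a test of loss.
4. Make the matching change to the list of effects in the Study Summary.

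The cost is a few sentences. No visits, participants or data are added.

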7.1 Sample Size Determination

We calculated power for comparing groups on change in SRS-2 total score (the primary outcome measure), using a standard approach for linear mixed models (Littell RC, Milliken GA, Stroup WW, Wolfinger RD, Schabenberger O. *SAS for mixed models [electronic resource]*. Cary, N.C.: SAS Institute, Inc.; 2006). We assumed that the mean differences observed in the trial by Singh et al. represented the true values (i.e., we assumed mean differences of 7, 20, 18.4, and 0.4 at weeks 4, 8, 12 and 16, respectively), and we assumed a constant standard deviation of 20, consistent with that observed by Singh et al. Furthermore, we assume within-participants across time correlation of 0.5 (a conservative value) and we assume no more than 15% loss distributed over the 16 weeks of follow-up. Under these assumptions, randomizing 27 participants to each group will provide at least 80% power for an overall test comparing groups across all time points using a two-sided 4 degree of freedom test at the 0.05 significance level.

For the exploratory microbiota analysis, we aim to include a subset of 30 subjects in the sample. In a recent randomized cross-over trial of the effects of broccoli consumption on microbiota composition in 18 healthy adults [Kaczmarek 2017*], participants consuming broccoli exhibited an increase in the ratio of Baceteroidetes to Firmicutes by 37% from baseline to end, compared to a 5% reduction during the control period (p=0.02). With 15 participants per group, we will have >80% power to detect a similar change in the ratio of Bacteroidetes to Firmicutes.

* Kaczmarek JL, et al. Broccoli consumption impacts the human gastrointestinal microbiota. The FASEB Journal, 2017. 31(1 suppl): p.965.

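### Section 7.2's linear-time model carries only 3 treatment degrees of freedom, so the 4-df overall test in 7.1 and 7.2 does not exist on it and the three-way effect cannot be separated

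*Combined protocol and SAP*

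**What the plan says.** Section 7.2 models the SRS-2 total score at Baseline and Weeks 4, 8, 12 and 16 as a function of treatment, time and their interaction, with age stratum and screening SRS-2 as covariates. Time is centred at Week 12, and "Individual intercepts and slopes will be estimated as random-effects variables, and will be allowed to correlate", so time enters as a number. The plan then adds "a time-varying variable representing treatment phase (0=treatment, 1=follow-up period) and we cross this variable with treatment, time, and treatment x time". It names three effects of interest: the treatment main effect (impact at the end of active treatment), treatment x time, and the three-way term, which it glosses as "treatment x time x treatment phase (i.e., treatment differences in change over time during follow-up period".

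The testing order begins with an overall test. The analyst is to "test for any differences between groups across all four groups using a 4 degree of freedom linear contrast of the model parameters". Then: "If this overall test is significant at the 5% level, we will then test for differences separately at each time point".

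Section 7.1 powers the same gate, described as "an overall test comparing groups across all time points using a two-sided 4 degree of freedom test at the 0.05 significance level", with separate assumed differences of 7, 20, 18.4 and 0.4 at Weeks 4, 8, 12 and 16.

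On which visit belongs to which phase, Section 3.1 sets 12 weeks of active treatment followed by 4 weeks of discontinuation. The primary endpoint text and Section 6.7 both place Week 12 at the end of active treatment. Week 16 is the only later visit.

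**The concern.** A contrast of model parameters cannot have more degrees of freedom than the model has independent treatment parameters. With a single follow-up visit, a follow-up level and a follow-up slope cannot both be estimated, yet 7.2 includes both for each arm.

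What is at stake is the gate for the primary hypothesis. As written it cannot be run on the stated model, so the analyst must change either the model or the degrees of freedom. The scale is open too. Section 7.1 says "We calculated power for comparing groups on change in SRS-2 total score" but lists differences by visit, and 7.2 does not say whether the overall test concerns differences at visits or differences in change from Baseline. One of the three effects the plan sets out to interpret also has no unique estimate. Section 7.2 applies similar models to CGI-Severity and RBSR, so the fault carries over to those outcomes.

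**Working it through.** **Inputs.** From 7.1: differences 7, 20, 18.4, 0.4; SD 20; correlation 0.5; 27 per arm; up to 15% loss; two-sided 0.05. From 7.2: visits at Weeks 0, 4, 8, 12, 16; time centred at Week 12. From 3.1, the primary endpoint text and 6.7: Week 12 is in the treatment phase.

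**1. The plan's power figure.** Take compound symmetry, Σ = 400(0.5 I + 0.5 J), so Σ⁻¹ = (I − J/5)/200 for four visits. The noncentrality is λ = (n/2) d′Σ⁻¹d.
- d′d = 49 + 400 + 338.56 + 0.16 = 787.72.
- (Σd)²/5 = 45.8²/5 = 419.53.
- d′Σ⁻¹d = (787.72 − 419.53)/200 = 1.841.
- n = 27: λ = 13.5 × 1.841 = 24.85; 4-df chi-square power 98.9%.
- n = 23 (27 × 0.85 ≈ 23): λ = 11.5 × 1.841 = 21.17; power 97.3%.

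The claim of at least 80% is met.

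**2. Coding of the design.**

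| Week | time | phase | phase x time |
|---|---|---|---|
| 0 | −12 | 0 | 0 |
| 4 | −8 | 0 | 0 |
| 8 | −4 | 0 | 0 |
| 12 | 0 | 0 | 0 |
| 16 | +4 | 1 | 4 |

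The last column is 4 x phase in every row. Multiplying by treatment gives treatment x time x phase = 4 x (treatment x phase). Of the eight columns (intercept, time, phase, phase x time, and each multiplied by treatment), two are redundant: rank 6 of 8. The four treatment columns have rank 3.

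**3. Fitted treatment differences.** Write the coefficients as a (treatment), b (treatment x time), c (treatment x phase) and g (three-way).
- Weeks 0, 4, 8, 12: a − 12b, a − 8b, a − 4b, a.
- Week 16: a + 4b + (c + 4g).

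Only a, b and the sum c + 4g are estimable. The differences at Weeks 4, 8, 12 and 16 therefore form a rank-3 set. Differences in change from Baseline are 4b, 8b, 12b and 16b + (c + 4g), which have rank 2. Week 16 minus Week 12 is 4b + (c + 4g), which is estimable.

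**4. Size if 4 df is kept regardless.** The 5% chi-square critical values are 7.81 on 3 df and 9.49 on 4 df. A rank-3 statistic referred to 9.49 rejects under the null with probability 2.3%.

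**5. Other codings.**
- *Week 12 as phase 1.* The treatment terms reach rank 4. But a is the difference at time 0 with phase 0, which would then be extrapolated from Weeks 0 to 8.
- *Actual visit days.* The design has full rank, but g is identified only by scatter in Week 16 timing. The documents give no visit window. Assuming a timing SD of 0.3 to 1 week, the standard error of g is about 15 to 4 points per week, against about 0.4 for treatment x time.
- *Visit as categorical.* A 4-df test exists, and the phase columns add nothing to the rank.

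**6. Power of the test the linear model supports.** Taking the Baseline difference as 0 (randomization), the 3-df test has λ = 26.9 and power 99.6% at 27 per arm, and λ = 22.9 and power 98.8% at 23 per arm.

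**The case against.** The strongest reply is that little is lost. Software will drop or sweep out the redundant columns, the fit is unaffected, and the global hypothesis of no treatment difference is still tested, on 3 df. The 4 may simply count the four treatment parameters rather than four visits, in which case the slip is one digit and one surplus term per arm. This largely stands as a statement about harm. It does not rescue the text: on either meaning of 4, the available rank is 3.

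The plan can also be read so that a 4-df test exists. The primary hypothesis dates discontinuation at Week 12, which might suggest coding that visit as follow-up. That contradicts the primary endpoint text and Section 6.7, and 7.2's own description of the treatment main effect as the impact at the end of active treatment. Actual visit days would also restore full rank, but 7.2 names its visits by nominal week, and the three-way term would then be very imprecise.

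A reader might infer more than the documents support:
- *That the trial is underpowered.* It is not; the stated power is exceeded on the plan's own assumptions.
- *That type I error is inflated.* Each candidate gate alone holds 5%. In a simulation with SD 20, 27 per arm, known covariance, complete data and no covariate adjustment, keeping whichever of a linear-time gate and its 4-df counterpart rejects gives 7.3% to 7.7%. Nothing in the plan proposes doing that.
- *That the random-effects structure conflicts with "We will use an unstructured covariance matrix".* That sentence can describe the covariance of the random intercept and slope, so no fault is shown there.

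**Conclusion.** The plan is wrong as written on this point and should be corrected before unblinding. On linear time, nominal weeks and Week 12 in the treatment phase, the treatment terms have 3 degrees of freedom (2 on change from Baseline), not 4, and the three-way effect cannot be separated from treatment x phase. If 4 df were used anyway, the gate would run at 2.3% instead of 5%.

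The consequence is limited. The primary analysis does not fail: the treatment effect at Week 12, treatment x time and all fitted visit differences are estimable. Error inflation would arise only if the choice among gates were left until data are seen. The rank result is algebra and does not depend on the assumed effects. The power figures assume compound symmetry at 0.5 and no covariate adjustment.

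**What to change.** Take one of two routes, and settle it before unblinding.

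**(a) Minimum change.** Keep linear time. Delete phase and treatment x phase, and keep time x phase and treatment x time x phase, which put a knot at Week 12. This spans the same fitted means with no redundancy, and the three-way term becomes the treatment difference in change of slope after Week 12. State 3 df in both 7.1 and 7.2, or 2 df if the gate is on change from Baseline.

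**(b) Keep the 4-df test that 7.1 powers.** Model visit as categorical with treatment x visit, retaining age stratum and screening SRS-2. Define the 4-df gate and the visit tests on one stated scale. Replace the three-way term with the treatment difference in Week 16 minus Week 12.

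In either case, correct the reference to four groups, since the trial has two arms, and carry the change into the similar models for CGI-Severity and RBSR.

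The cost is SAP wording; no new data or visits are needed. Route (b) has a somewhat larger Week 12 standard error: 20 × √(2/27) = 5.4, against 5.0 for the linear model, under compound symmetry 0.5, complete data and no covariate adjustment. The planned screening covariate would change both figures.

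### Section 7.2 reads the Week 12 effect off a straight line, so on section 7.1's own non-linear profile it misses the assumed difference by about 0.8 to 3.2 points, depending on the covariance

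*Combined protocol and SAP*

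**What the plan says.** Section 7.2 (Primary Hypotheses) models SRS-2 total at Baseline and Weeks 4, 8, 12 and 16 on treatment, time and their interaction, with age stratum and the screening SRS-2 as covariates. "Individual intercepts and slopes will be estimated as random-effects variables". A phase indicator is 0 on treatment and 1 in follow-up, and is crossed with the other terms. Time is centred at Week 12, and the reading of the coefficients follows: "Of interest will be the main effect of treatment (i.e., treatment impact at end of active treatment". The covariance is called unstructured, without saying whether this means the random effects or the residuals.

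The same section then describes an overall test with 4 degrees of freedom and, if that is significant at 5%, tests at the individual time points with estimated mean differences and 95% intervals. It names no visit factor, curvature term or check of linearity.

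Section 7.1 sets out the expected result: "we assumed mean differences of 7, 20, 18.4, and 0.4 at weeks 4, 8, 12 and 16, respectively". Under Primary Study Endpoints (section 3.1), the endpoint is the percent change in mean SRS-2 total from Baseline to Week 12.

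**The concern.** With time as a slope variable centred at Week 12, the treatment coefficient is the height at Week 12 of the fitted difference line. Only Week 16 falls in the follow-up phase, so the phase terms absorb that visit and the line is fitted to Baseline and Weeks 4, 8 and 12. The plan's own profile is not a line: it climbs steeply to Week 8 and then flattens. The coefficient labelled as the end-of-treatment effect therefore borrows from Week 8, where the plan expects the largest difference, and on that profile the error favours the product.

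The estimate and interval reported for the trial's main time point are at stake. The bias comes from the shape of the model, so a larger sample would not remove it.

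**Working it through.** **Inputs.** Differences of 7, 20, 18.4 and 0.4 (section 7.1). Baseline difference 0 (assumption: not stated as a number, but it follows from randomization). Section 7.1 also gives "we assumed a constant standard deviation of 20", "within-participants across time correlation of 0.5 (a conservative value" and "we assume no more than 15% loss distributed over the 16 weeks of follow-up". The correlation is read as equal between all visits. With 27 per arm, 15% loss leaves 0.85 × 27 = 22.95, or about 23. Week 12 is taken as part of the treatment phase.

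**The plan's own figure.** For four visits with variance 400 and correlation 0.5, the inverse covariance is (1/200)(I − J/5), where J is the matrix of ones.
- Sum of squared differences: 49 + 400 + 338.56 + 0.16 = 787.72.
- Squared sum divided by 5: 45.8²/5 = 419.53.
- Quadratic form: (787.72 − 419.53)/200 = 1.841.
- Noncentrality (n/2) × 1.841: 24.9 at 27 per arm and 21.1 at 22.95.
- Power of the 4-df F test: 98% and 95%. The stated power of at least 80% is confirmed as a lower bound.

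**Weights of the Week 12 coefficient.** For times −12, −8, −4 and 0 the mean is −6 and the sum of squares is 80. The line's value at 0 gives each visit the weight 0.25 + 6(t + 6)/80, that is −0.2, 0.1, 0.4 and 0.7. Generalized and ordinary least squares agree here under a random intercept and slope, because those columns lie in the span of the fixed design. They also agree under constant correlation.

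**Plan profile.**
- Week 12 estimate: 0.1 × 7 + 0.4 × 20 + 0.7 × 18.4 = 0.7 + 8.0 + 12.88 = 21.58, against 18.4 (+3.18, or 17%).
- Fitted differences at Weeks 0, 4, 8 and 12: 1.12, 7.94, 14.76 and 21.58, against 0, 7, 20 and 18.4.
- Baseline-to-Week-12 change from the same line: 21.58 − 1.12 = 20.46 (+2.06, or 11%).

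**Coverage under constant correlation.** The squared weights sum to 0.70 and the weights to 1. The per-participant variance is 200 × 0.70 + 200 = 340 unadjusted, or 240 after adjusting for screening (which removes 400 × 0.5² = 100).

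| | SE, 23 per arm | SE, 27 per arm | Coverage of 18.4 |
|---|---|---|---|
| Week 12 coefficient, unadjusted, √(680/n) | 5.44 | 5.02 | 91%, 90% |
| Week 12 coefficient, screening-adjusted, √(480/n) | 4.57 | 4.22 | 89%, 88% |
| Change from the line, √(720/n) | 5.60 | 5.16 | 93%, 93% |

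**Other covariances.** With AR(1) residuals, unadjusted, the Week 12 estimate is 20.2 at correlation 0.5 and 19.2 at 0.8. The bias is then about +1.8 to +0.8, with coverage of 94-95%.

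**Hypothetical transient benefit (0, 7, 20, 0).** This profile is not in the documents. It shows how the test behaves if an early effect has gone by Week 12.
- Constant correlation: the estimate is 0.7 + 8.0 = 8.7 where the truth is 0. The ungated Week 12 test rejects in 36-41% of trials unadjusted and 48-54% screening-adjusted (23 and 27 per arm).
- Constant correlation, behind the overall test (6,000 simulated trials per setting, screening-adjusted, 23 and 27 per arm): 31-37% if the overall test comes from the line model, 45-51% if it comes from free visit means.
- AR(1), unadjusted and ungated: 7-16%.
- Free visit means: 4.9% and 4.8% behind the gate.

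**Complete null.** In the same simulation the Week 12 test rejects in about 5% of trials, or about 2% behind the gate.

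**Can the written model give visit means?** At Week 16 centred time is 4, so phase × time equals 4 × phase throughout. The four treatment terms therefore have rank 3. They cannot describe free visit means or form a 4-df contrast.

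**The case against.** The strongest reply is that section 7.2 goes on to test each time point separately behind a 4-df overall test, and section 7.1 powers four separate visit differences. That suggests visit means, under which Week 12 is unbiased. As to intent, this stands. It does not settle the matter, because the written model has only three free treatment terms and section 7.2 ties the end-of-treatment effect to the main-effect coefficient.

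The +3.2 also depends on the covariance. The correlation of 0.5 is a power assumption, and one meaning of unstructured is a freely estimated residual covariance. The AR(1) figures show a smaller bias and almost nominal coverage. The primary hypothesis concerns change, for which the line is off by 2.1 under the same assumptions. Both points stand.

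A reader might infer that the plan's Week 12 test has an inflated false-positive rate in general. The documents do not support that. Type I error holds under the complete null, and a false Week 12 claim needs a real earlier effect that has disappeared by Week 12, which the plan nowhere assumes. A reader might also infer that the line always favours the product. It does so on the plan's profile, but a hypothetical late onset (0, 0, 0, 18.4) would give 0.7 × 18.4 = 12.9, an underestimate.

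**Conclusion.** The point holds in a bounded form. As written, the coefficient that section 7.2 calls the end-of-treatment effect does not estimate the Week 12 difference that section 7.1 assumes. It is +3.2 points off under a random intercept and slope or constant correlation 0.5, and about +0.8 to +1.8 off under AR(1) with correlation 0.5-0.8. It would be unbiased if visit means were intended, but the text does not provide them. The change from the line is +2.1 off under constant correlation.

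This rests on reading time as linear, which the slopes and the centring imply, on a Baseline difference of 0, and on Week 12 belonging to the treatment phase. The conclusion on power is not threatened. What needs correcting is which number, with which interval, is reported as the Week 12 effect.

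**What to change.** In section 7.2:
- Fit visit as a categorical factor with treatment × visit, and an unstructured within-subject covariance in place of random slopes.
- State how Baseline is handled, for example by constraining the arms to be equal there. The four post-baseline treatment contrasts then form the 4-df overall test that section 7.1 powers.
- Name the Week 12 contrast as the primary estimate, and keep the slope model as supportive.

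**Cost.** The text changes, but no data collection does. At 23 per arm, screening-adjusted, correlation 0.5, the nominal standard error rises from 4.57 to √(600/23) = 5.11. If Baseline is also used through the equality constraint, the conditional variance is 400 × (1 − 0.5/1.5) = 266.7, and the standard error about √(533.3/23) = 4.8.

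On the plan's profile, root mean squared error falls from √(4.57² + 3.18²) = 5.57 to 5.11 under constant correlation. Under AR(1), unadjusted, the two are about equal (5.97-5.93 for the line against 5.90). Simulated power for Week 12 behind the overall test is 97% at 27 and 95% at 23 per arm on the assumed profile (screening and Baseline as covariates). Five visits need 15 covariance parameters from 54 participants, so a small-sample degrees-of-freedom method should be named.
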